## 7. RATIONALE AND BACKGROUND

The novel coronavirus SARS-CoV-2 (severe acute respiratory syndrome coronavirus 2), the cause of coronavirus disease 2019 (COVID-19), has led to a global pandemic. AZD1222 (called Vaxzevria® in Europe) is a vaccine that was developed to prevent COVID-19.

Coronaviruses are enveloped viruses with positive-sense single-stranded RNA genomes. The spike glycoprotein is a coronavirus surface protein involved in receptor binding and mediating

virus entry into host cells during infection (Li 2016). AZD1222 is a recombinant replication-defective chimpanzee adenovirus expressing the SARS-CoV-2 spike glycoprotein. Development of AZD1222 was initiated by the University of Oxford with subsequent transfer of development activities to the Sponsor.

On 30 December 2020, the UK Medicines and Healthcare products Regulatory Agency (MHRA) provided authorisation for emergency supply of AZD1222, and on 29 January 2021, the European Commission granted conditional marketing authorisation for the vaccine. Now known as COVID-19 Vaccine AstraZeneca, the vaccine in both jurisdictions is indicated for active immunisation to prevent COVID-19 caused by SARS-CoV-2, in individuals aged 18 years and older. The vaccination course consists of 2 separate intramuscular injections. The second dose should be administered between 4 and 12 weeks (28 to 84 days) after the first dose. Since May 2022, a booster dose may be given at least 3 months after the second dose. A booster dose of AZD1222 can also be given to adults who have had 2 doses of an authorised mRNA COVID-19 vaccine but is beyond the scope of this study. At the national level, public health bodies may issue official recommendations, taking into account emerging effectiveness data and the limited safety data.

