### 9.1.1 Retrospective Cohort Design

A retrospective cohort of exposed subjects will be selected. Subjects will enter the exposed cohort upon their first vaccination with AZD1222. Subjects in the AZD1222 cohort will be matched, as applicable, to 3 different comparator cohorts: concurrent unvaccinated subjects, active comparators (ie, subjects vaccinated with an mRNA vaccine against COVID-19), and historical comparators enrolled in the study data sources during the pre-pandemic period (ie, from 2017 to 2018). The AZD1222 cohort will be matched, as applicable, independently to the 3 different comparator cohorts on calendar date of vaccination, age, sex, region, prior COVID-19, and status according to each of the 5 special populations (Section 9.2.1.2). Propensity scores (PSs) will be used to address confounding, balancing multiple covariates such as comorbidities, markers of healthcare utilisation and comedication between the vaccinated and the different comparator cohorts (Austin 2014, Webster-Clark et al 2021). Relative risk will be the main measure of effect, which will be estimated using incidence rate ratios (IRRs), prevalence proportion ratios (PPRs), or hazard ratios (HRs), depending on the analysis and outcome. Absolute risk difference measures will include incidence rate differences, prevalence proportion differences (PPD), and  $1 - KM^2$  differences.

In the cohort study, the initial plan was to use concurrent, rather than historical, comparator (unvaccinated) subjects because they are at risk for COVID-19, and COVID-19 may function as an important covariable in the analyses of several of the safety endpoints. Moreover, both healthcare-seeking behaviours and healthcare delivery during the pandemic differ from those during the pre-pandemic era. The potential challenge with this approach is that during the pandemic, concurrent unvaccinated subjects in the comparator group may themselves become vaccinated over time. Results from Interim Reports 1 and 2 confirmed that the duration of follow-up among concurrent unvaccinated subjects was short (median, < 2 months in all data sources) and probably not long enough to evaluate AESIs with unknown risk window—(those with a risk window that ends at 180 or 365 days). Thus, additional comparators for whom the follow-up is expected to be longer were requested by the PRAC and have been added to the

---

[figure not shown]
 KM, Kaplan-Meier estimate.

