#### 9.2.3.1 Cohort Design: Follow-up

Follow-up will start on the index date and end on the earliest of the following possible follow-up termination dates:

- The end date of the study period.
- The subject's enrolment termination date in the health plan or system.
- The subject's date of death.
- For the specific evaluation of each AESI:
  - The date of the first diagnosis of a specific AESI recorded after the index date, during the study period. For composite outcomes, follow-up will be censored at the date of the first occurrence of any of the components.
  - For the evaluation of AESIs with **known risk windows** (ie, those for which the end of the risk window is other than 180 or 365 days), the date on which the defined risk window for the last dose ends (the last dose was dose 1 if only 1 dose was received and dose 2 if 2 or more doses were received).
    - For subjects who received 2 doses of AZD1222, or of an mRNA vaccine, and were not censored due to an AESI or other censoring criteria before the second dose, a second risk window will follow the second dose; and for concurrent unvaccinated comparators or historical comparator subjects, a corresponding second risk interval will also apply, mirroring the timing of the second risk interval for the matched vaccinee (Figure 4). As previously noted, the start and duration of the risk windows will be specific to each outcome, corresponding to the period when the biologic effect of a vaccine is hypothesised to increase the risk for the particular AESI (Section 9.1.2). If an AESI occurs during a gap between doses, this AESI will not be included as an event in the study, and as stated above, the follow-up will be censored at the time of the AESI.
    - This risk window applies to both the vaccinee and matched comparator subjects.

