The PRAC AR for Interim Report 1 (7 July 2022) requested that the MAH discuss the need for additional data sources. As per results from this Interim Report 1, 5.8 million subjects included in the study have received at least one dose of AZD1222. The number of AZD1222 vaccinees and data sources included in the current study at this time is considered acceptable for the purpose of interpreting findings as continuous measures that are estimated with varying degrees of precision ([Rothman and Greenland 2018](#)). Therefore, no additional data sources are considered necessary.

**Table 5 Probability That the Upper 95% Confidence Limit of the Observed IRR Will Be Below 1.5, 2, 2.5, and 3 for Various Study Sizes of Vaccinated Subjects, Assuming That the True RR is 1 and the Ratio of Vaccinated-to-Concurrent Unvaccinated Person-time is 3 to 1**

Adverse event (duration of risk interval after each dose)	Estimated background rate per 100,000 PY	People vaccinated	Upper confidence limit of IRR			
			1.5	2.0	2.5	3.0
Anaphylaxis (VAC4EU 2021, Willame et al 2021)	6	1,000,000	0.04	0.05	0.07	0.08
(3 days)	6	2,000,000	0.05	0.07	0.09	0.12
	6	3,000,000	0.05	0.09	0.12	0.16
	6	4,000,000	0.06	0.10	0.15	0.19
	6	5,000,000	0.07	0.12	0.17	0.23
GBS (VAC4EU 2021, Willame et al 2021)	2	1,000,000	0.06	0.11	0.16	0.22
(42 days)	2	2,000,000	0.09	0.18	0.28	0.38
	2	3,000,000	0.11	0.25	0.40	0.53
	2	4,000,000	0.14	0.32	0.50	0.65
	2	5,000,000	0.16	0.38	0.59	0.75
Bell's palsy (Morales et al 2013) (42 days)	38	1,000,000	0.47	0.90	0.99	1.00
VTE a (Heit 2015) (42 days)	100	1,000,000	0.87	1.00	1.00	1.00

a This adverse event is a constituent of the composite AESI “thrombosis.”

Note: Calculations assume a true IRR of 1.0 and a ratio of 1-to-4 exposed to unexposed person-years. Calculations also assume that each person contributes 6 days of follow-up for anaphylaxis (3-day risk interval x 2 doses), 56 days for stroke (28-day risk interval x 2 doses), and 84 days (42-day risk interval x 2 doses) for all other adverse events (Rothman and Greenland 2018). Calculations follow the method of Rothman and Greenland (2018).

AESI, adverse event of special interest; GBS, Guillain-Barré syndrome; IRR, incidence rate ratio; PY, person-years; RR, risk ratio; VAC4EU, Vaccine monitoring Collaboration for Europe; VTE, venous thromboembolism.

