#### 9.7.6 Analysis of Incidence Rates

The analyses described below will address primary objective 3 and exploratory objective 1.

- For AESIs with **known risk windows** (those for which the end of the risk window is other than 180 or 365 days), crude IRs, and 95% CIs for each AESI will be estimated for the vaccinated cohort and the comparator cohorts. These analyses will combine person-time at risk after dose 1 and dose 2 (if it was received), using definitions of time at risk presented in Section 9.2.3.1. Exploratory analyses will report the IRs by specific dose.

For 2 specific AESIs, anaphylaxis and sudden death, since time to the event was not of interest, the prevalence proportions (PPs) and 95% CIs will be estimated.

- For AESIs with **unknown risk windows** (those with a risk window that ends at 180 or 365 days), cumulative incidence will be estimated using 1 – Kaplan-Meier survival curves starting at the index date. In addition, for AESIs with **unknown risk windows**, we will also describe the cumulative incidence over sequential time periods (eg, fortnights) to explore potential changes in risk over the follow-up period.
- In the primary analysis, IRs, PPs, and cumulative incidence of AESIs will be described for the AZD1222 cohort and for the 3 comparator cohorts (concurrent unvaccinated comparators, active comparators, and historical comparators) selected for comparative analyses (Section 9.7.3.3).
- For exploratory objective 1, in the AZD1222 matched cohort to active comparator cohort, the AESIs following a single dose of AZD1222 will be described.

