### 9.7.7 Crude and Adjusted Measures of Association: Cohort Design

The analyses described below will address primary objective 4 and exploratory objectives 2.

- The analysis will compare subjects vaccinated with AZD1222 with the concurrent unvaccinated comparators and historical comparators to estimate the effect of receiving any dose (a first or a second), under the assumption that the effect of either dose is homogeneous. The effect of each individual dose on AESIs, will be estimated as prior vaccine exposure may “prime” the immune system.
- For outcomes that have **known risk windows**, we propose to estimate crude and adjusted IRRs and IR differences with 95% CIs using Poisson regression models. Specifically, the IRRs would be estimated using Poisson regression with robust estimation of the variance to account for individuals who may contribute person-time at different points to the exposed and unexposed cohorts (Zou 2004). For anaphylaxis and sudden death, crude and adjusted PPRs and PPDs with 95% CIs will be estimated using Poisson regression models with robust estimation of the variance to account for individuals who may contribute person-time to the exposed and unexposed cohorts at different timepoints.
- For outcomes **with unknown risk windows**, we propose estimating crude and adjusted relative risks and absolute risk differences. The relative risk (HRs) and 95% CI will be estimated using Cox regression models with robust estimation of the variance time-to-event analyses (Allison 2010). Using Cox regression models allows the flexibility to potentially adjust for time-dependant covariates, such as intercurrent COVID-19 infection.
- Adjustment for confounding will occur using PS, either through PS matching or by analytic methods involving stratification or weighting, which will be specified in the SAP. In the event that important covariates remain imbalanced after final selection of the cohorts for comparative analyses, additional approaches for confounding adjustment will be considered, including double-robust methods (ie, including the covariate in the outcome model as a separate term) or through analyses that restrict the population to subjects with more similar baseline characteristics (eg, subjects without substantial comorbidity).

The analysis described below will address exploratory objective 3

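### For anaphylaxis and sudden death, the pooled any-dose prevalence proportion ratio against concurrent unvaccinated comparators exceeds 1 under no effect if, as its plain reading implies, the denominator is subjects at index

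*Protocol*

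**What the plan says.** - **Measure.** For these two events, Section 9.7.6 states that "since time to the event was not of interest, the prevalence proportions (PPs) and 95% CIs will be estimated". The statement sits under the item on AESIs with known risk windows, where "These analyses will combine person-time at risk after dose 1 and dose 2 (if it was received"). Section 9.7.7 adds: "For anaphylaxis and sudden death, crude and adjusted PPRs and PPDs with 95% CIs will be estimated using Poisson regression models". Table 1 gives the reason: the risk windows are extremely short.
- **Comparison.** The contrast with concurrent unvaccinated and historical comparators in Section 9.7.7 is meant "to estimate the effect of receiving any dose (a first or a second), under the assumption that the effect of either dose is homogeneous".
- **Second window.** For unvaccinated comparators, Section 9.2.3.1 says that "a corresponding second risk interval will also apply, mirroring the timing of the second risk interval for the matched vaccinee". The note to Table 5 (Section 9.5) assumes that "each person contributes 6 days of follow-up for anaphylaxis (3-day risk interval x 2 doses").
- **Follow-up.** Section 9.1.1 reports that follow-up among "concurrent unvaccinated subjects was short (median, < 2 months in all data sources"). Section 7 says: "The second dose should be administered between 4 and 12 weeks (28 to 84 days) after the first dose".
- **Censoring.** Section 9.2.3.1 ends a concurrent comparator's follow-up when that subject receives AZD1222. Section 9.7.1 confirms that censoring applies to individuals, not matched pairs. Censoring both members of a pair is a sensitivity analysis in Section 9.7.10.

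**The concern.** A vaccinee with two doses is observed in two windows. A matched comparator who is censored between the two dates is observed in only one. Each counts once in a proportion of subjects, so the vaccinated cohort has more opportunity for events over an equal denominator.

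Other AESIs with known windows use person-time, which absorbs this difference. Only anaphylaxis and sudden death lose that protection. The reason given in Table 1 does not cover the problem: a short window makes the timing of an event within it unimportant, but here a whole window is missing.

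Anaphylaxis is a listed safety concern (Section 7), and the concurrent unvaccinated comparison serves primary objective 4. A ratio above 1 that arises from the denominator could be read as a vaccine effect. Section 9.7.11 allows PPRs to be pooled across data sources, and pooling does not average out a bias that has the same direction in each.

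**Working it through.** **1. The plan's own anaphylaxis figure.** Inputs from Section 9.5 and Table 5: background rate 6 per 100,000 person-years, 3 days × 2 doses = 6 days per person, 5 million vaccinated, person-time ratio 3:1, true ratio 1.

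- Vaccinated events: a = 5,000,000 × (6/365.25) × 6/100,000 = 4.93. Comparator events: b = a/3 = 1.64.
- P(upper limit < U) = Φ(ln U / √(1/a + 1/b) − 1.96), where √(1/4.93 + 1/1.64) = 0.90.
- For U = 1.5, 2.0, 2.5 and 3.0 this gives 0.066, 0.117, 0.173 and 0.229. Table 5 has 0.07, 0.12, 0.17 and 0.23, so the figures reproduce.

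The planning therefore treats anaphylaxis as a rate ratio over two windows with unequal person-time. The analysis sections then use a measure with no time term.

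**2. Null value of the PPR with subjects at index as denominator.** Take N matched pairs (ratio 1:1, Section 9.2.1.1.3) and the same small risk r in every window for both cohorts.

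- Vaccinated events: N·r·(1 + p). Comparator events: N·r·(1 + p·s).
- PPR = (1 + p)/(1 + p·s). PPD = r·p·(1 − s).

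The PPR is above 1 whenever p > 0 and s < 1. Its ceiling is 2 (p = 1, s = 0). It does not depend on window length, so it applies equally to sudden death (days 0 to 6).

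**3. Size.** The protocol gives neither p nor s. Assumptions: p from 0.5 to 1, and exponential comparator follow-up with a median of 60 days, so that s = 2^(−d/60) for dose 2 at day d.

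| Dose 2 at day | s | Null PPR, p = 0.5 | Null PPR, p = 1 |
|---|---|---|---|
| 28 | 0.72 | 1.10 | 1.16 |
| 56 | 0.52 | 1.19 | 1.31 |
| 84 | 0.38 | 1.26 | 1.45 |

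The reported median is below 2 months, and a shorter one enlarges the shift. A 30-day median, for example, gives 1.19 to 1.31 at day 28 and 1.40 to 1.75 at day 84. A simulation of 20 million pairs with p = 1 and s = 0.5 gave 1.33, as the formula does (2/1.5).

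**4. Size against the interval, anaphylaxis.** With 5 million pairs, p = 1 and s = 0.5:

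- Expected vaccinated events are 4.93; expected comparator events are 4.93 × 1.5/2 = 3.70.
- PPR = 1.33. PPD = (4.93 − 3.70)/5 million = 0.25 per million.
- SE of the log ratio = √(1/4.93 + 1/3.70) = 0.69, so the 95% interval is roughly 0.35 to 5.1.

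The protocol gives no background rate for sudden death, so the same step cannot be done for it.

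**5. Whether existing provisions remove it.**

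- The exclusion in Section 9.2.1.1.3 covers events or censoring between the index date and the start of the risk window. Both windows start on day 0, so it does not reach subjects lost between the two doses.
- Robust variance changes standard errors, not the point estimate.
- Propensity scores built on covariates at index do not restore an unobserved window.

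**6. Null value under the proposed definition.** Dose 1: N·r/N in both cohorts, ratio 1. Dose 2: N·p·r/(N·p) against N·p·s·r/(N·p·s), ratio 1. The stratified ratio stays at 1 even if the background risk differs between the two windows.

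**The case against.** **The denominator is not written down.** The sentence on combining doses concerns person-time for rates, the 6 days in Table 5 is a planning input, and Table 1 traces the proportion to a statistical analysis plan that is not shown. If that plan counts dose windows at risk, the problem disappears. This stands as a limit. Even so, subjects are the natural denominator of a proportion that drops time, and the protocol itself fixes this measure for a pooled any-dose contrast.

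**Much is already planned.** Section 9.7.7 estimates each dose's effect, Section 9.9.1 promises relative measures by dose and names anaphylaxis (because of dose heterogeneity), and Section 9.7.10 includes pair censoring. The dose-1 estimate is essentially unaffected, and pair censoring brings the null ratio back to about 1.00. These would reveal the problem, but they leave the main PPR and PPD as they are.

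**The effect is small beside the noise.** For anaphylaxis this is correct, and Section 9.9.2 already warns of low precision. However, Section 9.7 bases interpretation on magnitude, precision and possible bias, so a known directional bias in the point estimate still matters.

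**Stronger readings that a reader might infer:**

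- *That the final report will show a visible excess of anaphylaxis, or a visible conflict with the historical comparison.* About 5 against 4 expected events cannot show either. Healthy-vaccinee bias or confounding (Section 9.9.1) could also offset the shift.
- *That the ratio would be about 1.6 or more.* At p = 0.9 that needs s near 0.2 (1.9/1.18 = 1.61), and the documents give no value of s.
- *That the 3:1 person-time ratio measures the bias.* With 1:1 matching and at most two windows per subject, the ceiling is 2.

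**Conclusion.** The point holds, conditional on the plain reading of the denominator. In the pooled any-dose comparison with concurrent unvaccinated subjects, the PPR for anaphylaxis and sudden death has a null value above 1, and the PPD one above 0. The direction follows from the protocol's own follow-up rules. The size rests on assumed p, assumed s and equal risk per window, as set out in the working.

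The historical comparison does not share the mechanism, because its members are not lost to vaccination. Nor does the comparative analysis with active comparators, which uses only the window after dose 2. This calls for a correction of wording before the final analysis; it does not undermine the study as a whole.

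**What to change.** In Sections 9.7.6 and 9.7.7, define PP, PPR and PPD for anaphylaxis and sudden death per dose window. The denominator for each window is the subjects under follow-up on its day 0. Obtain the pooled any-dose PPR and PPD stratified by dose. State that the dose-specific values are reported beside the pooled ones, as Section 9.9.1 already intends.

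There is no need to require both pair members to be under follow-up at dose 2. That rule would discard a share 1 − s of the vaccinated dose-2 windows, half of them at s = 0.5. It can remain the sensitivity analysis of Section 9.7.10.

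The change needs no new data. It costs a little more analysis work and a somewhat less precise pooled estimate. It removes the counting artefact only: comparators still unvaccinated at the dose-2 date may differ from those already censored, and the pair-censoring analysis remains useful for that question.

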### 9.2.1.2 Special Populations

In addition to the general study population, safety concerns will also be evaluated in prespecified subgroups for which information was deemed missing in the RMP.

- Women who are pregnant or breastfeeding
- Immunocompromised subjects
- Frail subjects with comorbidities (eg, chronic obstructive pulmonary disease, diabetes, chronic neurological disease, cardiovascular disorders)
- Subjects with autoimmune or inflammatory disorders
- Subjects who, at cohort entry, had recently received vaccines to prevent diseases other than COVID-19, such as pneumococcal infection, influenza, and shingles (herpes zoster).

Concepts to identify the special populations are listed in [Appendix C, Annex Table 3](#). Details on algorithms to identify each of these subgroups will be documented in a SAP.

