## **Appendix C Additional Information**

**Annex Table 1 Covariates Proposed to Define the Study Population and Cohorts**

Related to AZD1222 vaccination
Date of dose 1
Date of dose 2
Number of doses
Timing between doses
Related to non-AZD1222 vaccines against COVID-19
Receipt of any SARS-CoV-2 vaccine other than AZD1222
Date of vaccination
Duration of available look-back period
Earliest date of data availability
Exclusion and censoring criteria
Latest date of data availability
For each AESI: dates of occurrence
Date of death

AESI, adverse event of special interest; COVID-19, coronavirus disease 2019; SAP, statistical analysis plan; SARS-CoV-2, severe acute respiratory syndrome coronavirus 2.

Note: A final list of covariates and their operational definitions will be specified in the SAP.

**Annex Table 2 Covariates Proposed to Define Subgroups of Interest Included as Missing Information in the EU RMPa**

To identify women who are pregnant or breastfeeding
Pregnancy status at cohort entry (algorithms including pregnancy outcomes such as miscarriage or live birth will be used to determine duration of pregnancy)
Breastfeeding status at cohort entry (as available, or measured by proxy, such as first 6 months postpartum)
To identify immunocompromised patients
Receipt of organ transplantation
Specific white cell haematological neoplasias (eg, chronic lymphocytic leukaemia, chronic myeloid leukaemia, multiple myeloma)
Human immunodeficiency virus (HIV) infection
Primary immunodeficiencies (eg, chronic granulomatous disease [CGD])
Recent or current use of immunosuppressive medications, eg, cytotoxic chemotherapy, biologic immunomodulatory therapies, methotrexate, chronic corticosteroid use
To identify autoimmune and inflammatory disorders
Rheumatoid arthritis
Polymyalgia rheumatica
Systemic lupus erythematosus
Crohn's disease and ulcerative colitis
Other autoimmune and connective tissue diseases (eg, primary biliary cholangitis, systemic sclerosis, psoriasis, vasculitis)
Neuroimmune conditions (eg, multiple sclerosis, myelitis, previous GBS)
To identify frail patients with comorbidities
Indicators of frailty
Dispensing of or reimbursement for durable medical equipment (eg, wheelchairs, home oxygen)
Residence in long-term facility or nursing home
Hip fracture
Palliative care
Metastatic cancer
Cachexia
Dementia
Pressure ulcers
Bladder incontinence

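### Absolute risks for the 180- and 365-day AESIs are 1 minus Kaplan-Meier with death as censoring, which overstates the risk that occurs where mortality is high, chiefly in frail subjects

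*Protocol*

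**What the plan says.** Protocol section 9.7.6 fixes the estimator of cumulative incidence as 1 minus "Kaplan-Meier survival curves starting at the index date". It does so for one group of AESIs, described as "those with a risk window that ends at 180 or 365 days". Rate-based measures are assigned to the known-window AESIs, and prevalence proportions to anaphylaxis and sudden death.

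Section 9.1.1: "Absolute risk difference measures will include incidence rate differences, prevalence proportion differences (PPD), and" then 1-KM differences. Section 9.7.7 asks for absolute risk differences for the unknown-window AESIs without naming another estimator. So 1-KM and its differences are the only absolute-risk measures planned for this group.

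Section 9.2.3.1: "Follow-up will start on the index date and end on the earliest of the following possible follow-up termination dates". The list includes "The subject's date of death". Annex Table 1 places date of death under "Exclusion and censoring criteria".

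Section 9.7.9 applies analogous approaches to the special populations, one of which section 9.2.1.2 defines as "Frail subjects with comorbidities". Section 9.7.11 allows cumulative incidence to be pooled across data sources.

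No section treats death as a competing event. Section 9.9.1 discusses fatal events only for the SCRI design.

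**The concern.** Someone who has died can no longer develop the AESI. Kaplan-Meier treats death like loss of observation and assumes that the dead would have gone on to have events at the rate of the survivors. The resulting 1-KM is a hypothetical risk without death, and even that reading requires death to be independent of the AESI. It is never smaller than the proportion who experience the event, and the gap grows with mortality and with the length of follow-up.

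Both can be large here. Follow-up runs to 180 or 365 days after the last dose. The frailty indicators in Annex Table 2 include palliative care, metastatic cancer, cachexia and dementia. Section 9.5, writing about TTS, prefers absolute measures for judging public health impact and benefit-risk balance; that use calls for the risk that actually occurs.

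**Working it through.** The protocol states no risk or precision figure for this estimator, so there is nothing to reproduce.

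**Inputs**
- Horizons: 180 and 365 days (section 9.7.6, Table 3). With the second dose at up to 84 days (section 7), follow-up can reach 84 + 365 = 449 days from index.
- Annual mortality q: not given; assumed 1% to 40%.
- AESI hazard L: not given for these AESIs; assumed 10 to 1,000 per 100,000 person-years. Tables 5 and 6 give 2 to 100 per 100,000 person-years, for other AESIs.

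**Formulas** (constant hazards, death hazard M = -ln(1 - q), t in years)
- 1-KM, death censored: 1 - exp(-L t)
- Cumulative incidence with death competing: L/(L + M) x [1 - exp(-(L + M) t)]

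Example: L = 0.001, q = 20%, t = 1. M = 0.2231. 1-KM = 99.95 per 100,000. Competing-risk incidence = 0.001/0.2241 x (1 - exp(-0.2241)) = 89.59 per 100,000. Ratio 1.116.

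**Single-cohort risk**, L = 100 per 100,000 person-years, 365 days, per 100,000:

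| Annual mortality (assumed) | 1-KM | Death competing | Overstatement |
|---|---|---|---|
| 1% | 99.95 | 99.45 | 0.5% |
| 5% | 99.95 | 97.43 | 2.6% |
| 10% | 99.95 | 94.87 | 5.4% |
| 20% | 99.95 | 89.59 | 11.6% |
| 30% | 99.95 | 84.07 | 18.9% |
| 40% | 99.95 | 78.27 | 27.7% |

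At 20% mortality the overstatement is 5.6% at 180 days and about 14% at 449 days. The relative error hardly changes with L between 10 and 1,000. The absolute error does: at L = 10 and 20% mortality it is 10.00 versus 8.96, about 1 per 100,000.

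**Simulation check.** 2,000,000 subjects, L = 1,000 per 100,000 person-years, 20% mortality, one year: product-limit 1-KM 0.010053, observed proportion with the event 0.009014, ratio 1.115. The formula gives 995.02/891.98 = 1.116.

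**Risk difference**, one year, per 100,000:

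| AESI hazard, vaccinated vs comparator | Mortality, vaccinated vs comparator | 1-KM difference | Death-competing difference |
|---|---|---|---|
| 200 vs 100 | 20% vs 20% | 99.9 | 89.5 |
| 200 vs 100 | 10% vs 20% | 99.9 | 100.1 |
| 100 vs 100 | 10% vs 20% | 0 | 94.87 - 89.59 = 5.3 |

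The 1-KM difference is too large in the first row, marginally too small in the second, and too small in the third.

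**The case against.** The strongest reply is the last row of the second table. With no vaccine effect on the AESI hazard, 1-KM gives a difference of zero, while the competing-risk difference shows an excess of about 5 per 100,000 in the cohort that dies less. If mortality differs because of healthy-vaccinee selection or because 2017-2018 differs from the pandemic, Aalen-Johansen carries that into the AESI contrast. This stands: the change is not free of interpretive cost, and the cause-specific hazard ratio has to be read beside it. It does not make 1-KM the proportion affected.

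Other parts of the reply also stand:
- The mortality figures are assumed.
- Cohorts are matched on age, sex and special-population status, and the propensity score candidates include frailty markers and the Charlson index, so a twofold mortality difference should not be presumed.
- The frail group's comorbidity indicators also include diabetes and COPD, so its average mortality may be well below that of palliative patients.
- Section 9.1.1 makes relative risk the main measure. For these AESIs that is the Cox hazard ratio, for which censoring at death is acceptable.

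A reader might infer that risks for all five special populations will be materially too high. The protocol does not support that: nothing in it points to high mortality in pregnant or breastfeeding women or in recent recipients of other vaccines. Nor does it support a claim that the 1-KM difference is wrong in one known direction.

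The point cannot simply be left to the SAP, because the protocol itself names the estimator and the handling of death.

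**Conclusion.** The concern holds in limited form. For the 180- and 365-day AESIs the planned absolute risks are risks with death treated as censoring, and they exceed the risks that occur. Assuming constant hazards, the relative excess at one year is 0.5% at 1% annual mortality, about 5% at 10% and about 12% at 20%. It is negligible in a general population with mortality near 1%, and for rare AESIs it amounts to a few per 100,000 or less. It deserves correction because the same estimator is carried into the frail subgroup and other high-mortality strata. With equal mortality the risk difference is overstated in the same proportion; with unequal mortality the departure can go either way. The hazard ratios, and so the main effect measure, are not touched.

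**What to change.** 1. In sections 9.7.6 and 9.1.1, and so for the cumulative incidences pooled under 9.7.11, estimate absolute risks and their differences with the Aalen-Johansen estimator, death as a competing event, weighted where propensity score weights apply.
2. Keep the cause-specific Cox hazard ratio beside each risk difference, and say that the difference also reflects any mortality difference between cohorts.
3. Report deaths by cohort and subgroup.
4. If 1-KM is also shown, label it as the risk with death treated as censoring.
5. For windows that open late (day 14 for vaccine-associated enhanced disease, day 91 for fibromyalgia, day 183 for chronic fatigue syndrome), state that the risk is conditional on being alive and uncensored at the start of the window, because section 9.2.1.1.3 excludes subjects censored before it. A change of estimator does not remove that condition.

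The 12-day negative-control curves in 9.7.10.1 can stay as they are. At 20% annual mortality the overstatement is about M t/2 = 0.2231 x (12/365)/2 = 0.4%.

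The cost is recoding in the R and SAS scripts and variance estimation under matching with replacement, for which section 9.9.1 already has bootstrapping under evaluation. No new data are needed, since date of death is already a listed variable.
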